13.5 Interim Analysis

There are no planned interim analyses.

13.6 Exploratory Analysis

Treatment effectiveness may vary as a function of contextual as well as patient factors. In secondary analyses of the primary outcomes, care system indicators (Site 1, Site 2, Site 3), clinic (e.g., proportion of primary care patients eligible for OUD-CDS, proportion of clinic patients with government-sponsored insurance), and provider (e.g., waiver status, number of patients eligible for OUD-CDS, confidence in treating patients with OUD, intent to prescribe buprenorphine if waiver no longer required) characteristics may be added to the primary model as main effects and in interaction with the treatment group indicator to assess treatment heterogeneity due to contextual factors. Patient characteristics (e.g., race, ethnicity, age, estimated neighborhood income and education, documented heroin vs. oral opioid use) may be similarly added to assess treatment heterogeneity due to patient factors.

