13.1.5 Prediction Models

Aims 1 through 3 pertain to the effectiveness of the OUD-CDS intervention relative to UC, predicting that it will increase diagnosis, naloxone prescribing, and access to MOUD, and decrease ED visits and inpatient stays. These hypotheses will be tested using generalized linear mixed models to account for clustering of outcomes within eligible patients and randomized clinics, or using generalized estimating equations to compare event rates. Outcomes will be normalized via distribution-appropriate link functions (e.g., logistic-Normal, Poisson-Normal).

Clinic-randomized treatment group, care system and other predictors will be treated as fixed effects.

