13.2.2 Projected Number of Participants per Site

There must be at least 50 patients with or at high risk for OUD at an index visit at a randomized clinic for it to be included in the analyses. Based on the number of patients with study-eligible visits in the COMPUTE 1.0 pilot study, we expect this will be a low threshold for clinics to attain. The COMPUTE 1.0 intervention was implemented for six months among 55 randomized providers who practiced in 30 clinics. During that time, these providers saw between 14 and 137 patients (provider median = 77; 37-412 patients per clinic, clinic median = 163) who were eligible for the pilot OUD-CDS intervention. To the extent the COMPUTE 2.0 intervention is expected to collect outcome data on patients for 19 to 31 months in the randomized clinics, and study-eligible patients will be seen by all clinic providers, it is plausible to expect that 1,000 study-eligible patients could have index visits at many clinics.

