13.2.2.1 Statistical Power

A preliminary power analysis was conducted to estimate the minimum detectable difference in the likelihood of OUD diagnosis (H1.1), naloxone rescue kit order (H1.2) and MOUD order or referral for treatment (H2.2) within 30 days of the index visit, and the number of days covered by a MOUD prescription in the 90 days post-index (H2.2) among patients cared for in OUD-CDS relative to UC clinics (see **Section 13.4**). The power analysis relied on conservative assumptions regarding the numbers of randomized clinics (10, 30, 50) and of eligible patients (50 or 100 per clinic); a range of clinic intraclass correlations consistent with those observed for other process measures at HealthPartners (i.e., $ICC_{clin} = 0.01, 0.03, 0.05$); and central tendency estimates for the outcomes (2%, 5%, 10% and 20% or 70, 50, 30 days not covered in UC). Power estimates will be updated after Sites 2 and 3 are selected and preliminary data to inform analysis assumptions become available.

Effect size estimates for the binary outcomes were calculated using the NIH group randomized trial sample size calculator.[48] The difference in days covered was estimated using the Poisson regression module of PASS 11 software[49] after calculating an effective sample size (i.e., $N_{eff} = (n \text{ clinics} * m \text{ patients per clinic}) / (1 + (m-1) * ICC_{clin})$). In addition, the Poisson model power analysis was conducted to estimate the minimally detectable decrease in days NOT covered in the 90 days to post-index among OUD-CDS relative to UC patients to ensure that the estimated days in both groups remained between 0 and 90 days.

Table 3 summarizes the minimum detectable increases in outcome rates among OUD-CDS relative to UC patients given the aforementioned assumptions. Assuming 30 randomized clinics with 50 high risk patients each, that 5% of UC patients have an OUD diagnosis within 30 days of their index visit and $ICC_{clin} = 0.03$, the H1.1 analysis would be powered (power=0.80, $\alpha_2 = 0.05$) to detect a difference if $\geq 11.35\%$ (odds ratio = 2.43) of OUD-CDS patients have an OUD diagnosis within 30 days of their index visit. For an event occurring among 10% of UC patients given the

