13.3 Statistical Methods for Primary and Secondary Outcomes

This section provides an overview of the statistical methods to be employed in testing the primary and secondary outcomes. A more detailed description of the analysis may be found in the Statistical Analysis Plan. The Statistical Analysis Plan will provide more clarity about the underlying assumptions and methodological decisions regarding primary outcome analyses, including the extent to which either supplement alters the treatment effect.

Hypotheses for Aims 1 and 2 predict that the OUD-CDS intervention will increase the likelihood that patients at high risk of OUD are diagnosed with OUD (H1.1); and that among those at high risk or diagnosed with OUD it will increase the likelihoods that a naloxone rescue kit is ordered (H1.2) and that MOUD is ordered or the patient is referred to a provider who can order MOUD (H2.1), and the number of days covered by an MOUD prescription (H2.2). The hypotheses from Aims 1 and 2 will be tested using generalized linear mixed models so that the likelihood or counts of outcomes may be accurately estimated among OUD-CDS relative to UC clinics, accounting for the clustering of patients within randomized clinics. Binary outcomes (H1.1, H1.2, H2.1) will be normalized using a logistic-Normal link function, while it is anticipated that the count outcome (H2.2) will be normalized using a Poisson-Normal link function. The model will estimate fixed effects of OUD-CDS, care system and other covariates on outcomes, and random intercepts for clinics and patients (H1.1, H1.2, H2.1) or for clinics (H2.2).

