13.4 Significance Testing

The H1.1, H1.2 and H2.1 outcomes will be assessed 3 times for each patient – at the index visit (0 days), and 30 (for primary outcomes) and 90 days post-index. Outcomes that occur at an index visit will be coded as also having occurred by days 30 and 90. Similarly, outcomes that occur between days 1 and 30 will be coded as having occurred by days 30 and 90; and those occurring

between days 31 and 90 will be coded as having occurred by day 90. We expect that the documented actions that providers take will be overwhelmingly attributable to the index visit. Some actions that providers initiate at the index visit, such as placing a treatment referral order, may not be complete until considerations related to safety or availability are addressed. The primary outcome for H1.1, H1.2 and H2.1 will be assessed at 30 days so that these actions, likely initiated at the index visit, may be completed prior to assessing the outcome. It is possible that outcomes will not be documented for patients who have post-index visits within 90 days at non-participating clinics. We assume that these eventualities will be rare and equally likely across treatment groups.

Because virtually all of the information pertinent to the H1.1, H1.2 and H2.1 outcomes will be captured by the day 30 measure, the primary hypothesis test for these models will compare the likelihood of the day 30 outcome by treatment group. The primary hypothesis test for the H2.2 outcome will compare the likelihood of the day 90 outcome by treatment group. These comparisons will be evaluated using a two-sided test with a Type I error rate of 5%. Comparisons at other time points will aid understanding of how relative differences in OUD-CDS versus UC settings may increase or decrease in the short term. For example, OUD-CDS might initiate a course of provider actions that otherwise would not occur (increase) or merely hasten action that eventually takes place in UC settings (decrease).

The Aim 3 outcomes represent counts of events that accrue over the post-index observation periods. The event rates in OUD-CDS versus UC clinics will be evaluated using a two-sided test with a Type I error rate of 5%.

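### Section 13.6 allows provider-level modifiers in a model with no provider random effect; if outcomes cluster by PCP within clinic, those exploratory interaction tests are anti-conservative

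*Combined protocol and SAP*

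**What the plan says.** Section 13.6 names, among the characteristics that may be tested as modifiers, "provider (e.g., waiver status, number of patients eligible for OUD-CDS, confidence in treating patients with OUD", followed by intent to prescribe buprenorphine if no waiver were required. It says such "characteristics may be added to the primary model as main effects and in interaction with the treatment group indicator". The wording is permissive and the section is headed exploratory. The synopsis (2.1, Secondary Analyses) is firmer: it commits to assessing whether effectiveness varies with provider characteristics, among others, but fixes no model.

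The model that would receive these terms is set out in section 13.3, with "random intercepts for clinics and patients (H1.1, H1.2, H2.1) or for clinics (H2.2"). Section 13.1.5 says the models are to "account for clustering of outcomes within eligible patients and randomized clinics" and treats treatment, care system and other predictors as fixed effects. Neither section mentions a provider random effect or a provider-level robust variance. Sections 10.2 and 13.1.4 assign each patient to the clinic of the index visit, but no rule ties a patient to one PCP.

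Section 5.2 plans a related analysis: for PCPs in intervention clinics, whether engagement with the tool is associated with patient outcomes. No model is given for it.

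**The concern.** A provider characteristic such as waiver status takes one value for all of a PCP's patients. If those patients also share unmeasured features of that PCP's practice, their outcomes are correlated. A model that clusters only on clinic treats them as independent once the clinic effect is removed. The patient intercept does not help: it handles the repeated assessments of one patient at days 0, 30 and 90 (section 13.4), not correlation between patients of the same PCP. The standard error of the provider term and of its interaction with treatment is then too small.

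The plan gives reason to expect some clustering by PCP. Section 8.2 leaves use of the tool at each encounter to the PCP. Table 2 in section 11.2 makes the standard deviation among clinicians, in process and outcome measures, something to be monitored. At stake are statements such as the tool working better for waivered PCPs, which readers would take as guidance for roll-out.

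**Working it through.** **Step 1. The plan's own figure.** Section 13.2.2.1 gives no figure for provider interactions, so the check starts from its H1.1 example: 30 clinics of 50 patients, usual-care rate 5%, clinic ICC 0.03, power 0.80, two-sided alpha 0.05, minimum detectable rate 11.35% (odds ratio 2.43).

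- Design effect = 1 + (50 − 1) × 0.03 = 2.47.
- Effective n per arm = 15 × 50 / 2.47 = 303.6.
- Power for 5% v 11.35%: 0.816 (normal) or 0.787 (t, 28 df). Odds ratio 2.43.
- Minimum detectable rate: 11.2% (normal) to 11.5% (t).

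The figure is reproduced. It accounts for clinic clustering only, which is right for an arm comparison randomised by clinic.

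**Step 2. Inputs for the provider interaction.**

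- From the documents: 30 clinics, 1:1; clinic ICC 0.03, applied here on the latent scale; a usual-care rate of 10%, one of the plan's scenarios; at least 3 full-time PCPs per clinic (section 8.1); planning minimum of 50 patients per clinic; expected enrolment above 10,000 (section 14.3.1), or about 10,000/30 = 333 per clinic.
- Assumed: PCP ICC from 0 to 0.10 (latent scale); 5 PCPs per clinic in the larger layout; 30% of PCPs with the trait; a 5% two-sided test, since 13.6 states no alpha for these interactions.
- Layouts: 3 PCPs × 17 patients (51 per clinic, 1,530 in all) and 5 PCPs × 67 patients (335 per clinic, 10,050 in all).

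**Step 3. Simulation with no true interaction.** Logistic mixed models were fitted by penalised quasi-likelihood, with a Wald test at 1.96, once with a clinic intercept only and once with clinic and PCP intercepts. There was one binary outcome per patient, so the patient intercept and the three time points were not simulated. As a cross-check:

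actual alpha = 2 × [1 − Φ(1.96 / √(1 + (m − 1) × ICC))]

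Here m is patients per PCP and ICC is on the observed scale. For example, with m = 67 and ICC 0.0186, the design effect is 1 + 66 × 0.0186 = 2.23 and alpha is 0.189.

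| Layout | PCP ICC, latent (observed) | Clinic only, simulated | Clinic only, formula | Clinic + PCP, simulated |
|---|---|---|---|---|
| 3 × 17 | 0 (0) | 0.047 | 0.050 | 0.035 |
| 3 × 17 | 0.01 (0.0034) | 0.053 | 0.056 | 0.039 |
| 3 × 17 | 0.03 (0.0105) | 0.064 | 0.070 | 0.051 |
| 3 × 17 | 0.05 (0.0186) | 0.079 | 0.085 | 0.050 |
| 3 × 17 | 0.10 (0.0412) | 0.100 | 0.128 | 0.064 |
| 5 × 67 | 0 (0) | 0.046 | 0.050 | 0.032 |
| 5 × 67 | 0.01 (0.0033) | 0.074 | 0.076 | 0.038 |
| 5 × 67 | 0.03 (0.0106) | 0.164 | 0.133 | 0.056 |
| 5 × 67 | 0.05 (0.0186) | 0.180 | 0.189 | 0.062 |
| 5 × 67 | 0.10 (0.0404) | 0.268 | 0.306 | 0.038 |

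Runs per row: 1,000 to 1,500 (3 × 17) and 500 (5 × 67). The Monte Carlo standard error is about 0.006 to 0.010 in the first layout and 0.009 to 0.020 in the second. The formula is approximate, because the clinic intercept absorbs part of the PCP variation; the two columns agree in direction and rough size.

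**Step 4. Reading the table.** With no PCP clustering there is no inflation. At the planning minimum it is negligible to modest. At the expected enrolment it is material from a latent ICC of about 0.03. A PCP intercept brings error back to 0.032 to 0.064.

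**The case against.** The strongest reply has four parts.

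- **The analysis is optional and exploratory.** Section 13.6 says characteristics may be added and attaches no decision rule. This stands, and it limits the weight of the point. But the synopsis does commit to assessing modification by provider characteristics, and the primary model is the only one the text offers for it.
- **The inflation rests on a provider ICC that the documents never give.** This stands in full. A reader might infer that these tests are certain to be anti-conservative; the documents support only the conditional statement.
- **At the sample size used for power, the effect is small.** True for 50 patients per clinic. But section 13.2.2 calls that a low threshold and thinks 1,000 plausible at many clinics. In the pilot, over six months, "these providers saw between 14 and 137 patients (provider median = 77").
- **Section 13.3 defers detail to a separate Statistical Analysis Plan that is not in the supplied text.** It might add a provider level, so the point applies to the text as it stands.

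Two stronger readings are tempting. One is that the effective sample is the number of providers. The numbers contradict this: an error of 0.18 corresponds to variance inflation of (1.96/1.341)² = 2.14, so 10,050 patients carry the information of about 10,050/2.14 ≈ 4,700, far more than the 150 PCPs in that layout. The other is that section 5.2 also plans provider-by-treatment interactions. It does not: its interaction paragraph lists care-system, clinic and patient factors, and its PCP analysis is an association within intervention clinics.

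**Conclusion.** The point holds in conditional form. As written, section 13.6 would place provider-level modifiers in a model with no provider level. If outcomes cluster by PCP within clinic, the interaction tests reject too often.

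The size is unknown because the provider ICC is unknown. Over assumed latent ICCs of 0 to 0.10, a nominal 5% test has actual error of about 5% to 10% at the planning minimum, and about 5% to 27% at roughly 10,000 patients. These ranges also rest on the assumed 5 PCPs per clinic (larger layout), 30% of PCPs with the trait, and a 10% outcome rate.

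A reader might infer that the primary result is at risk. It is not: treatment is assigned by clinic and the clinic intercept is in the model. The point concerns only how far provider-modifier findings can be trusted, and it should be settled before those analyses are run.

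**What to change.** In section 13.6, state that any model containing a provider-level covariate, or its interaction with treatment, will add a random intercept for the PCP seen at the index visit, nested in clinic (or use provider-level robust variance). The same sentence supplies the missing rule linking each patient to one PCP. Apply the same term to the PCP-engagement association analysis in section 5.2. Leave the primary arm comparison as it is.

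The cost is one or two sentences, one extra variance term, and the index-visit PCP identifier in the analysis file. Intervals for provider modifiers become wider where PCPs differ. Where they do not, the test may be slightly conservative: 0.032 to 0.035 in the simulations with a PCP ICC of 0.

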13.7 Missing Data and Dropouts

We expect person-based missingness to be extremely rare. Patients are unlikely to be aware that their data are being used for this research. They will not be consented and are unlikely to request that their data be excluded from analyses. Only patients who have requested that their data not be used for research and appear on site-maintained opt out lists will be excluded.

The primary data source for the Aim 1 through 3 hypotheses will be gathered from EHR-based data repositories at each participating site. The stored EHR data elements required for calculating the primary and secondary outcomes are extracted from live production tables. Medical care costs for Aim 4 will come from administrative claims systems that are relied upon for reimbursement of medical care services. The absence of documentation of a care process, vital sign, or medication should not be interpreted as a missing value but rather as indicative of a care process or test not having been performed or medication not prescribed within the health system. Likewise, absence of utilization indicated by billing claims almost always indicates that the utilization (such as a hospitalization) did not occur. Truly missing field-based observations (e.g., OUD diagnosis assigned, action not observed) will be extremely rare, undetectable and assumed to be missing at random.

13.8 Demographic and Baseline Characteristics

Demographic and clinical variables available in the EHR at the index visits will be summarized for all enrolled study participants, overall and by site and treatment group. Descriptive summaries of the distribution of continuous baseline variables will be presented with percentiles (median, 25th and 75th percentiles), and with mean and standard deviation. Categorical variables will be summarized in terms of frequencies and percentages.

13.9 Safety Analysis

We will assess the rates of ED use, hospitalization and opioid overdoses that occur in intervention and control clinics during each patient's observation period. The rate at which each of these outcomes occurs per patient-year will be compared across clinics using generalized estimating equations. Clinic-aggregated counts of ED visits and inpatient stays will be normalized using a Poisson-Normal link function, and the intercept offset by the log of patient-years within the clinic. The model will estimate fixed effects of OUD-CDS, care system and other covariates on the rate of each outcome per patient-year. Should it be feasible, we will also collect and estimate the rate at which these events occurred in the year prior to each patient's index visit so that treatment group differences in pre-post changes in event rates can be quantified (i.e., treatment by time interaction).

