2.4 Treatment/Assessment/Intervention and Duration

The OUD-CDS provides clinical guidance to PCPs in the screening, diagnosis and treatment of OUD, along with common comorbid conditions, and will display for patients with OUD or at high risk for OUD in intervention primary care clinics during each site's intervention period (see timeline). PCPs are also able to access the OUD-CDS in EPIC for patient encounters for which it did not display (e.g., new patient visits). Patient follow-up time from the date of index visit is estimated to range from 18 to 31 months.

The OUD-CDS will be tested and evaluated prior to implementation, in the early implementation phase, and during the maintenance phase at each site by a combination of qualitative data collection, monitoring of use rates and PCP surveys at all time points.

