Potential Risks and Benefits. There is a small but important risk that the OUD-CDS could provide the wrong treatment advice at the wrong time. As with other clinical decision tools, the OUD-CDS makes suggestions for patient care that are meant to supplement but not supersede clinical judgment. PCPs can choose to follow or not follow the guidance of the CDS at any given

time in any given patient encounter. PCPs will be trained to let the research team know via the Feedback Tab in the CDS when their clinical judgment leads them to a different action than that suggested by the CDS. These events will be monitored in real time by the treatment team and the CDS algorithms adjusted if there are found to be errors. Every clinical encounter requires medical judgment and poses some element of risk to patients. In the situation of a PCP who is unfamiliar or uncomfortable with OUD, use of the CDS will likely make care safer by providing suggestions to screen and assess for OUD using validated tools, and to encourage referrals when patients are classified as high risk. We will not be encouraging buprenorphine use in non-certified providers, and this will be reinforced in PCP training on the CDS. For buprenorphine-certified providers, the use of the CDS may improve the likelihood of using MOUD in high-risk situations; however, the risks of MOUD are generally considered lower than untreated OUD in high-risk situations. This is a minimal risk study and the risk to a patient who is not receiving MOUD greatly exceeds the risk of the CDS intervention. Overall, the potential benefits of providing the OUD-CDS to intervention clinics, which include the ability to improve the identification of patients at-risk for OUD, to guide screening and diagnosis of OUD, and to guide treatment selection and prescription of MOUDs or referrals for people with OUD, ultimately increasing access to OUD treatment for patients with OUD in primary care, outweigh the potential risks outlined above.

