6.2 Duration of Study and Visit Schedule

Primary care clinics will be randomized within each health care system to receive or not receive access to the OUD-CDS. Once OUD-CDS is implemented in each health care system, its algorithms automatically identify eligible patients in all randomized intervention and UC clinics, independent of any PCP actions. PCPs in clinics with CDS access are anticipated to have access to the OUD-CDS intervention through May 2024, depending on factors such as healthcare system leader preference. In UC clinics, the OUD-CDS will run silently in the background over the same time period, collecting data without displaying. There is no study-determined visit schedule; rather, patient visits will be jointly determined by the patient and PCP. We plan to stop collecting outcome data in October 2023 at all sites. We anticipate patient observation periods of 19 to 31 months from date of index visit, depending on the site. Having the OUD-CDS run from implementation through the end of the observation period in all randomized clinics in each health care system ensures that identical methods are used to identify study-eligible patients and track patterns of OUD-related care so that we may quantify the impact of the OUD-CDS on OUD identification and care.

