7.2 Study Timeline

After receiving Center for the Clinical Trials Network (CCTN) approval of the final protocol, approximately 9-12 months of trial preparation activities will elapse prior to commencing enrollment (“go-live”) at Site 1. The intervention at Site 2 is anticipated to begin 6-9 months after go-live date at Site 1, and the intervention at Site 3 will begin 12-15 months after the go-live date at Site 1. Selection of Geisinger as Site 2 and Essentia as Site 3 occurred subsequent to the initial CCTN approval of the final protocol and initial IRB submission. Trial preparation will include obtaining Institutional Review Board (IRB) approval, customizing the OUD-CDS for each healthcare system, harmonizing data elements for EHR installation at each site, installing of EHR custom code at each site, recruiting and randomizing primary care clinics at each site, conducting PCP training at each site, integration of CDS into workflow at each site, and completing baseline PCP surveys at each site.

As noted previously, the COVID-19 pandemic delayed implementation by approximately 8 months. Accrual periods will range from 7 to 18 months based on site. During the accrual period, the study team will monitor accrual rates to determine when a sufficient number of patients have been enrolled to support the analysis plan. If enrollment is lower than expected, we may choose to extend the accrual period up to 3 additional months (through January 2023). Observation will begin with index dates at each site and are anticipated to continue through October 2023.

Anticipated Accrual + Observation Periods per Site:

- HealthPartners – April 2021 to Oct 2023 (31 months)
- Geisinger – Dec 2021 to Oct 2023 (22 months)
- Essentia – April 2022 to Oct 2023 (18 months)

Anticipated Accrual* Periods per Site:

- HealthPartners – April 2021 to Oct 2022 (18 months)
- Geisinger – Dec 2021 to Oct 2022 (10 months)
- Essentia – April 2022 to Oct 2022 (7 months)

* We may extend the accrual period an additional 3 months based on enrollment trends.

COMPUTE 2.0 Study Timeline

Study Timeline	Year 1		Year 2				Year 3				Year 4				Year 5		
	2019		2020		2021		2022		2023		2024						
	Quarter	3	4	1	2	3	4	1	2	3	4	1	2	3	4	1	2
Phase 1: Development Phase																	
Finalize protocol, obtain IRB approval (Site 1)																	
Obtain IRB approval at Sites 2 & 3																	
Customize OUD-CDS for each partner site																	

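### The Section 13.9 safety model pools each patient's whole follow-up, so a harm concentrated soon after the index visit would be diluted; a supplementary 0–90 day rate would close that gap in sensitivity

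*Combined protocol and SAP*

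**What the plan says.** Section 13.9 assesses "rates of ED use, hospitalization and opioid overdoses that occur in intervention and control clinics" over each patient's observation period. The method is: "The rate at which each of these outcomes occurs per patient-year will be compared across clinics using generalized estimating equations". Counts are aggregated by clinic, with "the intercept offset by the log of patient-years within the clinic", so early and late patient-time enter one denominator. Where feasible, a contrast with the year before index is added, but its post-index side is again the whole period. Apart from adding overdoses, the model is the one that Section 13.3 gives for the Aim 3 efficacy hypotheses on ED visits and inpatient stays.

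The process outcomes are handled differently. Section 13.4 measures H1.1, H1.2 and H2.1 at 0, 30 and 90 days, and explains: "We expect that the documented actions that providers take will be overwhelmingly attributable to the index visit". The risk named in Section 4.1 arises at an encounter: "There is a small but important risk that the OUD-CDS could provide the wrong treatment advice at the wrong time".

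Three places give the length of follow-up:
- Section 2.4: "Patient follow-up time from the date of index visit is estimated to range from 18 to 31 months".
- Section 6.2: "We anticipate patient observation periods of 19 to 31 months from date of index visit, depending on the site".
- Section 7.2 ends accrual in October 2022 and says: "Observation will begin with index dates at each site and are anticipated to continue through October 2023". A patient indexed at the end of accrual therefore has about 12 months, or about 9 if accrual is extended to January 2023.

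Section 2.5 gives the DSMB overdose, hospitalization and ED rates by site and blinded arm, with no time window stated. Section 14.16.2 says that adverse events are not collected.

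**The concern.** Benefit is measured in windows close to the index visit. Harm is measured only as an average over follow-up, most of which lies well after that visit. If the tool caused an excess of overdoses or acute-care visits in the first weeks, the excess would be spread over a year or more of other patient-time, and the estimate would lie close to 1.

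Because the same model also carries the efficacy hypotheses, which predict fewer ED visits and hospitalizations, an early excess and a later reduction would be netted against each other in one coefficient. With no adverse event collection, these routine event rates are the main by-arm information on patient harm. It is therefore worth asking which patterns of harm they could show.

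**Working it through.** **1. The plan's own figure.** No power is stated for the safety comparison. The nearest design figure is in Section 13.2.2.1: 30 clinics of 50 patients, 5% in usual care (UC), ICC 0.03 and 80% power give a detectable rate of 11.35%. Check with design effect 1 + 49 × 0.03 = 2.47, 750 patients per arm and 28 df (t values 2.048 + 0.855 = 2.903). Solving p − 0.05 = 2.903 × √[2.47 × (p(1 − p) + 0.05 × 0.95)/750] gives p = 11.42%. This reproduces the figure closely enough.

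**2. Mean follow-up.** With uniform accrual, take the midpoint between the longest follow-up at each system (31, 22 and 18 months, Section 7.2) and 12 months: 21.5, 17 and 15 months.

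**3. Dilution.** If the rate is multiplied by R for w days after index and is unchanged afterwards, the average ratio over follow-up T is 1 + (R − 1) × w/T.
- Doubling for 90 days (3 months): 1 + 3/21.5 = 1.14, 1 + 3/17 = 1.18, 1 + 3/15 = 1.20.
- Doubling for 30 days: 1.08 at 12 months, 1.05 at 18 and 1.03 at 31.

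**4. Offsetting.** As an illustration over 18 months, take a doubling for 3 months and then a 20% reduction for 15: (3 × 2.0 + 15 × 0.8)/18 = 1.00.

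**5. What Table 3 implies.** With 30 clinics of 100 patients and ICC 0.01, an event with 20% UC risk must reach 26.28%, a ratio of 1.31. Treat this roughly as a rate ratio over 18 months (548 days). A harm confined to 90 days would then need R = 1 + 0.314/(90/548) ≈ 2.9. A harm confined to 30 days would need about 6.7.

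**6. Power, whole period against 0–90 days.** Inputs from the documents are 30 clinics (15 per arm), about 5,000 patients per arm (Section 14.3.1 expects more than 10,000 in total) and a two-sided 5% level (Section 13.4, for the same model). Inputs assumed, because the documents give none:
- T = 18 months and between-clinic CV 0.1–0.3.
- UC rates per patient-year: ED 0.5–1.0, hospitalization 0.2, overdose 0.005 or 0.02.
- Overdispersion φ over the whole period: ED 3, hospitalization 1.5, overdose 1.0–1.2.
- φ in the window: ED and hospitalization 1.2, overdose 1.0–1.2.

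The test statistic is log(E1/E0) / √[φ(1/E0 + 1/E1) + 2 CV²/15], with noncentral t on 26 df. Example for hospitalizations with R = 1.5 over 90 days:
- Whole period: E0 = 0.2 × 5,000 × 1.5 = 1,500. E1 = 1,500 + 0.5 × 246.4 = 1,623. Ratio 1.08.
- Window: E0 = 0.2 × 5,000 × 90/365.25 = 246.4. E1 = 369.6.

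| Outcome (UC rate per year) | R over 90 days | Whole period | 0–90 days |
|---|---|---|---|
| ED (0.5–1.0) | 1.5 | 10–38% | 88–100% |
| ED (0.5–1.0) | 2.0 | 24–90% | about 100% |
| Hospitalization (0.2) | 1.5 | 9–27% | 79–98% |
| Hospitalization (0.2) | 2.0 | 24–74% | about 100% |
| Overdose (0.02) | 1.5 | 7–9% | 25–32% |
| Overdose (0.02) | 2.0 | 14–24% | 63–76% |
| Overdose (0.005) | 2.0 | 8–10% | 23–27% |

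For a doubling that lasts only 30 days, the whole-period test has about 7–19% power for ED visits, 7–14% for hospitalizations and 5–7% for overdoses. A matched 30-day window has 99–100%, 95–99% and 12–28%.

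**The case against.** A reader might infer that the plan itself expects harm at the index visit, and so contradicts itself by averaging over follow-up. The documents do not support that. The sentence in Section 13.4 concerns documented diagnoses, orders and referrals. It says nothing about when harm would occur, and the 30-day point is there to let actions begun at index be completed. The tool keeps displaying through the intervention period (Section 2.4), and post-index visits remain targeted visits (Section 4.1). A whole-period rate is a legitimate match to continuing exposure.

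A reader might also infer that short-term harm would go unseen. That is too strong:
- The DSMB receives the same rates by blinded arm. Its early tables would contain mostly short follow-up and so less dilution.
- PCP feedback is the direct route for reporting wrong advice. It comes through the tool, however, and so has no usual-care comparator.
- All-cause death and overdoses are also compared as secondary outcomes, again over the whole period.
- A 90-day doubling of ED visits may well be detected as planned (24–90%).

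The window is no cure-all either. With 2 overdoses per 100 patient-years, no overdispersion and CV 0.2–0.3, a sustained rate ratio of 1.5 gives the whole-period test 73–86% power and a 90-day test 29–31%. A doubling limited to 30 days gives the 90-day test only 16–17%. For overdoses, sparse events limit power as much as dilution does.

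Finally, Section 13.3 refers to a more detailed analysis plan. If that document contains a windowed safety rate, the point falls away; none appears in the text reviewed.

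All of this narrows the point. It does not supply a modelled early-window comparison, and it does not separate early harm from later benefit.

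**Conclusion.** The point holds as a gap in sensitivity to early harm. It is not an error in the whole-period estimand. The dilution follows from the Section 7.2 dates and uniform accrual alone: a 90-day doubling averages to about 1.14–1.20. The power figures also rest on assumed event rates, overdispersion, clinic variation and about 10,000 patients. Under those assumptions the gain from a window is large for ED visits and hospitalizations. For overdoses it is material only for large effects at the higher assumed rate.

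Whether harm would in fact be early is not known from the documents, which is why the window should supplement the planned rate and not replace it. Nothing in Section 13.9 says that a ratio near 1 would be reported as evidence of safety. Without an early rate, though, such a ratio could not be distinguished from an early excess that had been averaged away. The change is worth making because it is cheap and removes nothing.

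**What to change.** In Section 13.9:
- Keep the whole-period rate as planned.
- Add, as a prespecified supplementary analysis, the same model with events and patient-time limited to days 0–90 after index, for ED visits, hospitalizations and overdoses.
- Add a descriptive 0–30 day rate.
- Report events, patient-time, rates by arm and confidence intervals beside the whole-period result. Counts matter for overdoses: at 2 per 100 patient-years the window holds about 25 events in the UC arm, or fewer than 2 per clinic.

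In the DSMB tables of Section 2.5, show the 0–90 day rates by blinded arm. Separately, reconcile the follow-up ranges in Sections 2.4 and 6.2 with the Section 7.2 dates, which imply a minimum of about 12 months.

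The cost is analysis-plan wording and one more run of an existing model on dated events that are already being extracted. The downsides are fewer events and wider intervals in the window, and one more safety comparison to interpret. For a harm spread evenly over follow-up, the whole-period rate remains the better measure.
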